10.1 Study Endpoints

Primary endpoint:

- Number of participants with successful PET-based detection of ER-positive breast cancer and metastases

Other endpoints:

None

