10.2. Accrual estimates

We anticipate enrolling 20 patients in total.

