10.3 Analyses Plans

As this is an initial feasibility pilot, and we have no control over the biopsy process, we will only estimate the per-lesion sensitivity of ^{68}Ga -RM2 PET-based in detecting the known ER+ lesions.

There will be at least 20 ER+ lesions, and we expect that the PET sensitivity will be at least 80%. A sample of 20 will provide 90% power at one-sided 5% error to demonstrate that a sensitivity of 80% is greater than chance performance. A sample of 25 will provide 80% power to demonstrate sensitivity of 75%, which we believe is the minimum that would justify further study.

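### Section 10.3 claims 90% power at one-sided 5% error with 20 lesions but gives no number for chance and no test; at a 50% null, no cutoff on 20 lesions delivers both

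*Combined protocol and SAP*

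**What the plan says.** Section 10.3 (Analyses Plans) limits the analysis to estimation: "we will only estimate the per-lesion sensitivity of" the PET method for known ER+ lesions. It then sets out what it expects: "There will be at least 20 ER+ lesions, and we expect that the PET sensitivity will be at least 80" per cent. Two power sentences follow.

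The first concerns the minimum lesion count: "A sample of 20 will provide 90% power at one-sided 5% error to demonstrate that a sensitivity of 80% is greater than chance performance". Its null is given in words only, as chance. Neither 10.3 nor any other section gives a number for it, a named test or a rejection cutoff.

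The second concerns a larger count and a lower sensitivity, and restates neither the null nor the error rate: "A sample of 25 will provide 80% power to demonstrate sensitivity of 75%, which we believe is the minimum that would justify further study".

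Section 10.2 adds only the enrolment figure: "We anticipate enrolling 20 patients in total".

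**The concern.** The two power sentences are the plan's only quantitative support for its sample size. To check them, a reader must infer both the value of chance and the test.

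The natural guess is a 50% null. With so few lesions, the number detected moves in whole steps, and each step changes the error and the power by several points. A power figure from a smooth approximation may therefore match no rule that could be applied to 20 lesions. The sample size would then be justified by a pair of operating characteristics that the study cannot have.

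**Working it through.** **Inputs from 10.3.** n = 20; sensitivity under the alternative p1 = 0.80; one-sided error 0.05; stated power 90%. The sample is read as lesions, because the analysis is per lesion and the preceding sentence counts lesions.

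**Assumptions, not in the documents.** Null p0 = 0.50; lesions independent.

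**Step 1: reproduce the stated 90%.** Normal approximation, null variance for the cutoff, alternative variance for power, no continuity correction.

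- Standard error under the null: √(0.5 × 0.5 / 20) = 0.1118
- Standard error under the alternative: √(0.8 × 0.2 / 20) = 0.0894
- Cutoff: 0.5 + 1.645 × 0.1118 = 0.684, which is 13.68 lesions out of 20
- Power: Φ((0.800 − 0.684) / 0.0894) = Φ(1.298) = 90.3%

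This matches the stated 90%. With a continuity correction the same method gives 84.6%.

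**Step 2: exact error and power.** A cutoff of 13.68 lesions cannot be applied; in practice it means 14 or more. For a rule that rejects at k or more, error = P(X ≥ k | 20, 0.5) and power = P(X ≥ k | 20, 0.8), both binomial.

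- Error at k = 15: (15504 + 4845 + 1140 + 190 + 20 + 1) / 2^20 = 21700 / 1048576 = 2.07%
- Error at k = 14: (21700 + 38760) / 1048576 = 60460 / 1048576 = 5.77%

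| Reject at | True one-sided error | Power at 80% |
|---|---|---|
| 13/20 or more | 13.2% | 96.8% |
| 14/20 or more | 5.8% | 91.3% |
| 15/20 or more | 2.1% | 80.4% |
| 16/20 or more | 0.6% | 63.0% |

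Error and power both fall as the cutoff rises, so the table settles the question. Every cutoff with error of 5% or less has at most 80.4% power, and every cutoff with at least 90% power has at least 5.8% error.

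**Step 3: dependence on the assumed null (20 lesions, exact, error held at 5%).** The 14/20 cutoff keeps error at or below 5% for nulls up to 49.2%, and the 15/20 cutoff up to 54.4%.

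| Null | Cutoff | Power at 80% |
|---|---|---|
| 45% | 14/20 | 91.3% |
| 49% | 14/20 | 91.3% |
| 50% | 15/20 | 80.4% |
| 55% | 16/20 | 63.0% |
| 60% | 17/20 | 41.1% |

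**Step 4: dependence on the lesion count (null 50%, exact).** Power at 80% is 89.1% with 21 lesions (15 or more), 86.7% with 22 (16 or more) and 92.8% with 23 (16 or more, error 4.7%). Twenty-three is the smallest count that meets both limits.

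**Step 5 (secondary): the 25-lesion sentence.** This needs the further assumption that the 50% null and the one-sided 5% carry over. With p1 = 0.75:

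- Normal approximation: cutoff 0.5 + 1.645 × 0.1 = 0.6645; power Φ((0.75 − 0.6645) / 0.0866) = 83.8%, above the stated 80%
- 18/25 or more: error 2.2%, exact power 72.7%
- 17/25 or more: error 5.4%, exact power 85.1%

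**The case against.** The strongest reply is that the approximation is standard and 10.3 never promises an exact test. An uncorrected score test accepts 14/20 (z = (14 − 10)/√5 = 1.79, one-sided p = 0.037), and so does a mid-p test (0.039). Either has 91.3% power, and the excess over nominal error is 5.8 − 5 = 0.8 points. On that view, setting 80.4% against 90% compares one test with another. This stands as a limit on the size of the problem. It does not rescue the sentence, which pairs its power with 5% error: at 14/20 the error is above 5%, and the text does not say so.

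A second reply is that the result is fragile. A null of 49.2% or lower meets the stated pair, as do 23 lesions, and 10.3 expects 20 lesions as a minimum. This also stands. It is equally the reason to write the null down, because a one-point change from 49% to 50% moves exact power from 91.3% to 80.4%.

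A third reply is that 10.3 does name a null, as chance performance. That is correct; what is missing is its value.

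A reader might infer that the 90% was miscalculated, or that the pilot is too small for its purpose. The documents support neither. The 90% follows from a recognised formula, and the plan neither schedules a test nor makes any action depend on one.

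**Conclusion.** The power sentence is wrong as written, with chance read as 50% and lesions taken as independent. Exactly 20 lesions give either 80.4% power at 2.1% true error or 91.3% power at 5.8% true error. The first is 9.6 points short of the stated power; the second is 0.8 points over the stated error. The 50% is an inference, though it is the value at which a common approximation returns the stated figure.

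The 25-lesion sentence carries less weight. Its shortfall (72.7% against 80%) appears only under the exact test and only if the unstated null and error rate carry over. It should not be read as a second, independent error.

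Severity is minor to moderate. The justification of the sample size is affected; conduct is not, because no decision rule depends on these figures.

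**What to change.** Change the wording of 10.3 only, in one of two ways.

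1. **Keep a power statement.** State the null (50%, if that is what chance meant) and the test (exact one-sided binomial at 5%, lesions treated as independent), then restate power with cutoff and true error. With 20 lesions: reject at 15 or more, true error 2.1%, power 80% if sensitivity is 80%. With 25 lesions: reject at 18 or more, true error 2.2%, power 73% if sensitivity is 75%.
2. **Replace the power sentences with precision.** This fits a plan that will only estimate sensitivity. The exact (Clopper-Pearson) 95% interval is 56% to 94% if 16 of 20 lesions are detected and 59% to 93% if 20 of 25 are.

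The first option costs a less favourable stated power; the second gives up the power claim. Neither needs more participants or a change in conduct.

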^{68}Ga -labeled DOTA-4-amino-1-carboxymethyl-piperidine-D-Phe-Gln-Trp-Ala-Val-Gly-His-Sta-Leu-NH₂ (^{68}Ga -DOTA-Bombesin or ^{68}Ga -RM2, formerly also known as BAY86-7548) is a synthetic bombesin receptor antagonist, which targets gastrin-releasing peptide receptors (GRPR) (3). Stoykow and colleagues reported the use of ^{68}Ga -RM2 in 15 patients with breast cancer. A total of 13 of 18 tumors demonstrated strongly increased ^{68}Ga -RM2 uptake compared to normal breast tissue (defined as PET-positive). All PET-positive primary tumors were ER- and PR-positive (13 of /13) in contrast to only 1 of 5 PET-negative tumors. Mean SUV_{max} of ER-positive tumors was 10.6 ± 6.0 compared to 2.3 ± 1.0 in ER-negative tumors ($P = 0.016$). In a multivariate analysis including ER, PR, HER2/neu and MIB-1, only ER expression predicted ^{68}Ga -RM2 uptake (model: $r^2 = 0.55$, $p = 0.025$). Normal breast tissue showed inter- and intraindividually variable, moderate GRPR binding (SUV_{max} 2.3 ± 1.0), while physiological uptake of other organs was considerably less except pancreas. Of note, ^{68}Ga -RM2-PET/CT detected internal mammary lymph nodes with high ^{68}Ga -RM2 uptake ($n = 8$), a contralateral axillary lymph node metastasis (verified by biopsy) and bone metastases ($n = 1$; not detected by bone scan and CT). This study demonstrated that ^{68}Ga -RM2-PET/CT is a promising imaging method in ER-positive breast cancer. *In vivo* GRPR binding assessed by ^{68}Ga -RM2-PET/CT correlated with ER expression in primary tumors of untreated patients (4).

We conducted a pilot phase evaluation of ^{68}Ga -RM2 in prostate cancer patients under an RDRC-approved protocol at Stanford University. Ten men (age range: 60 to 83 year-old; mean \pm SD: 73.1 ± 6.9) with biochemical recurrence of prostate cancer (PSA range: 3.7 to 36.4; mean \pm SD: 12.5 ± 9.8) were enrolled. PET/MRI images were acquired at

42 to 51 minutes (mean \pm SD: 47.2 ± 3.2) after injection of 3.6 to 4.1 mCi (mean \pm SD: 3.7 ± 0.2) of ^{68}Ga -RM2.

Biodistribution and localization of ^{68}Ga -RM2

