2.4 Study Design

This is a pilot study enrolling up to 20 participants with ER+ breast cancer, either at initial diagnosis prior to surgery or at suspected recurrence. Eligible participants will undergo baseline assessments at enrollment. Study participants will receive ^{68}Ga -RM2 and undergo a PET/MRI scan. All patients will first be seen by a Stanford Cancer Institute physician and then referred if appropriate on clinical grounds to [name] or his colleagues for this study. The following steps will take place.

1. Participants will be given a copy of the consent form s/he signed.
2. Participant will be asked to drink 1 to 2 glasses of water before arrival at the clinic
3. Vital signs (heart rate, blood pressure) will be recorded
4. Participant will be injected IV with $140 \pm 20\%$ mBq of ^{68}Ga -RM2
5. Participant will void immediately prior to the scan
6. Data acquisition will begin with a dedicated scan of the breasts, followed by a vertex to mid-thighs scan. First, localizer MRI scans will be performed to define the table positions and then MR structural imaging and diffusion weighted imaging will be performed simultaneously with PET imaging. After the dedicated scan of the breasts, a whole-body combined PET/MRI acquisition will be initiated with 3 to 5 table positions at a 2 to 4 minute acquisition time per table position.
7. Vital signs (heart rate, blood pressure) will be recorded again at the completion of the study, and the patient will be dismissed.
8. Participants will be contacted at 24 to 72 hours following the scan in order to collect record any adverse events.

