2.4.2 Endpoints

Primary Endpoints

- Number of lesions identified on ^{68}Ga -RM2 PET/MRI
- Correlation of ^{68}Ga -RM2 uptake and ER positivity on biopsy (when done as clinically indicated)

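### Section 10.3 claims power against chance from known ER+ lesions alone, with no stated null; scoring the unaffected breast already in the scan would supply the missing comparison, as a supplement to sensitivity.

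*Combined protocol and SAP*

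**What the plan says.** Section 10.3 (Analyses Plans) limits the analysis to estimating per-lesion sensitivity in known ER+ lesions. It gives as reasons that this is a first feasibility pilot and that the investigators do not control biopsy. It assumes "There will be at least 20 ER+ lesions" and that "we expect that the PET sensitivity will be at least 80"%. It then says: "A sample of 20 will provide 90% power at one-sided 5% error to demonstrate that a sensitivity of 80% is greater than chance performance". No null value, test or cut-off is given. The same paragraph names 75% sensitivity as the least that would justify further study.

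Other sections bear on this:

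- **Section 3.1:** every participant has biopsy-proven ER+ breast cancer, at initial diagnosis or at suspected recurrence.
- **Section 2.4:** "Data acquisition will begin with a dedicated scan of the breasts, followed by a vertex to mid-thighs scan". Both breasts are therefore imaged.
- **Section 5.3:** readers blinded to medical history and other imaging tabulate lesions by consensus. No call per breast and no background uptake value is requested.
- **Sections 2.4.2, 2.4.3 and 10.1:** the endpoints are "Number of lesions identified on ^{68}Ga -RM2 PET/MRI", the correlation of uptake with ER positivity on biopsy, and the number of participants with successful detection.
- **Section 2.1:** the earlier breast cancer study of this tracer defined PET-positive relative to normal breast tissue. It also reported: "Normal breast tissue showed inter- and intraindividually variable, moderate GRPR binding".

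**The concern.** Sensitivity is measured on positives only. If calls carried no information about disease, the expected sensitivity would simply be the readers' rate of calling tissue positive. That rate is the chance level, and a set of known lesions cannot reveal it. A value of 50% would follow if readers were forced to choose which side is affected, but Section 5.3 sets no such task. A sensitivity above 50% may then be reported as better than chance when the study holds no data on how often tumour-free tissue is called positive.

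The missing information is largely within reach. In participants with one-sided breast disease, the other breast is in the same dedicated scan, yet no section plans to score or measure it. The plan's own background treats normal breast as the comparator for positivity and describes its uptake as variable.

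**Working it through.** **Inputs.** From Section 10.3: n = 20 lesions, one-sided α = 0.05, sensitivity p1 = 0.80, stated power 90%. The null p0 is not given; 0.50 is assumed. Lesions are treated as independent.

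**1. Reproducing the 90%.** Normal approximation, null variance under H0, alternative variance under H1, no continuity correction:

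power = Φ{[(p1 − p0)√n − z√(p0(1 − p0))] / √(p1(1 − p1))}
= Φ{[0.30 × 4.472 − 1.645 × 0.50] / 0.40}
= Φ{(1.342 − 0.822) / 0.40} = Φ(1.298) = 0.903.

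The required n by the same formula is 20. With a continuity correction, power is 0.846. So 50% is the implied null.

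**2. Exact binomial, n = 20, p0 = 0.50.**

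| Rule | Error: P(X ≥ r given 0.50) | Power: P(X ≥ r given 0.80) |
|---|---|---|
| r = 15 | 2.1% | 80.4% |
| r = 14 | 5.8% | 91.3% |

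No cut-off gives both an error of at most 5% and 90% power.

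**3. Dependence on the unstated null.** For the rule of at least 15 of 20, the probability of success when calls are unrelated to disease and made at rate q is P(X ≥ 15 given 20, q):

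| q | 0.40 | 0.50 | 0.55 | 0.60 |
|---|---|---|---|---|
| Probability | 0.2% | 2.1% | 5.5% | 12.6% |

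The documents do not give q. The true error could be below or above the nominal 5%.

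**4. What the unaffected breast would add.**

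*False-positive rate.* Exact (Clopper-Pearson) 95% limits: for 0 of 20 the upper limit is 1 − 0.025^(1/20) = 16.8%; for 2 of 20 the interval is 1.2% to 31.7%.

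*Paired calls.* Exact one-sided 5% McNemar test. Let s = 0.80 be the tumour-side call rate and f the unaffected-side call rate (unknown), with the two calls assumed independent. Discordant pairs favour the tumour with probability s(1 − f) and the other side with probability f(1 − s). Power is averaged over the binomial number of discordant pairs:

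| Pairs | f = 0.10 | f = 0.20 | f = 0.30 | f = 0.40 |
|---|---|---|---|---|
| 12 | 95% | 83% | 64% | 44% |
| 15 | 99% | 92% | 77% | 56% |
| 20 | >99% | 98% | 91% | 73% |

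The number of usable pairs is also unknown, because no section gives laterality.

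**5. Why this cannot replace sensitivity.** With true sensitivity of only 50% and f = 0.05, the same paired test is significant with 92% probability at 20 pairs. A significant side difference is therefore compatible with sensitivity well below the 75% minimum.

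**The case against.** The strongest reply is that Section 10.3 plans estimation only. The power sentence supports the sample size, no decision rule follows, and a one-sample test against a fixed 50% has a perfectly well-defined error rate. That stands. A reader might infer that no 5% error can exist in this design whatever test is used; the documents do not support that. What remains is that the 50% is unstated and has no claim to be the chance level.

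A reader might also infer that the result could easily be inflated by free calling, since a call rate of 70% would meet 15 of 20 with 41.6% probability. Nothing in the documents points to such rates. Readers are blinded to history and other imaging, a known lesion counts only if that lesion is found, and Section 2.1 reports SUVmax of 10.6 ± 6.0 in ER-positive tumours against 2.3 ± 1.0 in normal breast. The true chance level may lie below 50%, which would make the implied test conservative. The plan simply gives no way to tell.

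It is tempting, too, to replace the sensitivity analysis by the paired test. That would abandon the 75% benchmark and leave out metastases, which belong to the objective and the endpoint.

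Finally, the control is imperfect. Figure 2 shows a bilateral case, some participants with suspected recurrence may have had breast surgery, and no reference standard is planned for the unaffected breast. MRI is read in the same examination, so a side difference need not come from the tracer. These limits stand, and they confine the paired analyses to a supporting role.

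**Conclusion.** The point holds as a gap in wording together with an inexpensive improvement. The 90% is not an arithmetic error: it is 90.3% under an assumed 50% null and an approximate formula. Exact power at a true 5% level is 80.4%. Meeting that null would show sensitivity above 50%; it would not show that readers distinguish tumour from normal tissue, because no tumour-free unit is scored.

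The unaffected breast can fill part of that gap from scans already planned. How much depends on two unknowns, the number of one-sided participants and the control-side call rate. With 15 pairs, 80% tumour-side calls and independence, paired power runs from 99% at a 10% control-side rate to 77% at 30%. The documents do not show that the study's sensitivity estimate is invalid, and it should remain the main result.

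**What to change.** **Section 10.3, main analysis.** Either delete the comparison with chance, or restate it as a test against an explicit fixed null with its exact cut-off, error and power. Keep per-lesion sensitivity with an exact 95% confidence interval as the main estimate, read against the 75% minimum. For scale, 16 of 20 gives 56.3% to 94.3%.

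**Section 5.3.** Have the same blinded readers record a positive or negative call for each breast, and SUVmax in the lesion and in the mirrored region of the unaffected breast.

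**Section 10.3, supporting analyses in participants with one-sided breast disease.**

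- The false-positive rate in the unaffected breast with its exact confidence interval.
- The exact paired comparison of tumour-side and unaffected-side calls.
- The mean log ratio of lesion to unaffected-breast SUVmax with its 95% confidence interval.

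Use the 12-month chart review in Section 6.3 as the reference for the unaffected breast.

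**Cost.** Wording in two sections and a few minutes of measurement per scan, with no new scan, reader or participant. The control is unavailable in bilateral disease or after removal of the other breast. It does not cover metastases, and it does not separate the tracer's contribution from that of the MRI.

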3.1 Inclusion Criteria

Inclusion Criteria Yes must be checked to be eligible	Yes	No	Supporting Documentation
1. ≥ 18 years-old			
2. Biopsy proven ER+ breast cancer, either at initial diagnosis prior to surgery or at suspected recurrence.			
3. Able to provide written consent			
4. Karnofsky performance status of ≥ 50 (or ECOG/WHO equivalent)			
5. Females must be not be pregnant per urine pregnancy test			

3.2 Exclusion Criteria

Exclusion Criteria No must be checked to be eligible	Yes	No	Supporting Documentation
1. Inability to lie still for the entire imaging time			
2. Inability to complete the needed investigational and standard-of-care imaging examinations due to other reasons (severe claustrophobia, radiation phobia, etc)			
3. Any additional medical condition, serious intercurrent illness, or other extenuating circumstance that, in the opinion of the Investigator, may significantly interfere with study compliance.			
4. Metallic implants (contraindicated for MRI)			

*All subject files must include supporting documentation to confirm subject eligibility. The method of confirmation can include, but is not limited to, laboratory test results, radiology test results, subject self-report, and medical record review.

Statement of Eligibility

By signing this form of this trial I verify that this subject is [**eligible** / **ineligible**] for participation in the study. This study is approved by the Stanford Cancer Institute Scientific Review Committee, the Stanford IRB, and has finalized financial and contractual agreements as required by Stanford School of Medicine's Research Management Group.

Principal Investigator or Sub-Investigator:	Date:
Printed Name:	

Secondary Reviewer Signature:	Date:
Printed Name:	

Study Coordinator Signature:	Date:
Printed Name:	

x
